4.5 Patient consent for future access to archival tissue

Patients participating in the MARECA study will also be able to provide optional consent to donate their archived cancer tissue samples or slides for a potential research project in line with one of the study objectives (i.e. to determine the feasibility of designing a future potential translational study). The tissue samples will be pseudonymised. For the present study, participating centres will be not be required to access/process/store/retrieve any tissue sample any differently to current standard of routine clinical care. Consent for future

21

IRAS ID: 285389

The MARECA study Protocol version 4.0 25/05/2022

tissue sample or slide access will allow examination of the following potential research questions;

-Genomic/transcriptomic/proteomic comparison of archival tumour tissue from the primary cancer with that of the recurrent cancer. This will enable distinction of a new primary cancer from a true recurrence. This will be compared against the current clinical classification to determine if patient prognosis differs.

-Facilitate transfer and storage of these tumour samples in a centralised HTA approved tissue bank for future translational research studies with a focus on identification of biomarkers that predict treatment resistance.

If funding is obtained for the potential follow on translational studies, new ethics, R and D contracts and protocols will be made available to participating units, but patient consent will be retained from this study.

4.6 Patient inclusion and exclusion criteria

4.6.1 Inclusion criteria

- Female or male patients more than 18 years old. Treated for previous unilateral or bilateral breast cancer (invasive cancer including all histological subtypes as well as ductal carcinoma in situ) with curative intent.
- No previous evidence of distant metastatic disease.
- Recently (within the last 6 months) diagnosed with new ipsilateral breast cancer locoregional recurrence (biopsy proven invasive cancer including all histological subtypes or ductal carcinoma in situ) +/- distant metastasis.
- Able to provide written informed consent.
- A *minimum of 3 months interval* between the resection surgery for the original cancer and the diagnosis of locoregional recurrence. There will be *no maximum interval time period*.

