4.6.2 Exclusion criteria

- Patients where the new breast cancer diagnosis is in the contralateral breast.
- For patients who present with new bilateral breast cancer, the side with no previous cancer will be excluded.

- Patients diagnosed with distant metastatic disease with no evidence of LRR.
- Patients diagnosed with angiosarcoma.
- Patients with previous history of non-breast cancer treatment that was non-curative in intent
- Patients who have had previous ipsilateral surgery for atypia, benign conditions, or phyllodes tumour and other breast sarcomas AND no previous ipsilateral primary breast cancer resection.
- Patients under 18 years old.
- Patients lacking capacity to provide written informed consent.

5. Data collection

The following dataset will be collected prospectively during the 24 months patient recruitment phase. Data regarding the management of LRR will be collected prospectively as the patient's care progresses.

- 1. Patient demographics (at the time of LRR diagnosis) collected will include;
 - 1.1 Centre name and ID
 - 1.2 Age (years)
 - 1.3 Current menopausal status (pre-menopausal, post-menopausal, perimenopausal)
 - 1.4 BMI
 - 1.5 Smoking status (non-smoker, ex-smoker, current smoker)
 - 1.6 Patient performance status (0 to 4; based on Eastern Cooperative Oncology Group score)
 - 1.7 Family history risk as defined by NICE guideline; CG164[65] (unknown / population risk / moderate risk / high risk / BRCA mutation positive / other known germline breast cancer susceptibility gene pathogenic mutation- e.g. TP53 gene mutation)

2. Treatment detail about the original breast cancer

Surgery

- 2.1 Date of original breast cancer surgery
- 2.2 Screening or symptomatic diagnosis
- 2.3 Age at original diagnosis

- 2.4 Type of breast surgery (none / breast conserving surgery / mastectomy + immediate breast reconstruction / mastectomy and delayed reconstruction/ mastectomy with no reconstruction)
- 2.5 If breast conserving surgery was performed for invasive lobular cancer, was MRI performed (Yes/No/Not applicable)
- 2.6 What was the original tumour location (upper inner quadrant / upper outer quadrant / lower inner quadrant / lower outer quadrant / subareolar or central)
- 2.7 Type of axillary surgery (none / sentinel lymph node biopsy / axillary node clearance / axillary node sampling / targeted axillary dissection)

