- 3.52 Receipt of other targeted treatment (Yes/No; if Yes, please specify)

6. Data validation and quality assurance

Data collected on each patient must be recorded by the Principal Investigator, or his/her designee, as accurately and completely as possible. The Principal Investigator is responsible for the timing, completeness, legibility, accuracy and signing of the data entry on REDCap database and the CRF. The Clinical Investigators must allow study staff access to any required background pseudonymised data from hospital records (source data e.g. medical records) on request.

All fields MUST be completed. All data submitted must be verifiable in the source documentation. These may include, but are not limited to, hospital records (from which medical history and previous and concurrent medication may be summarised into the REDCap database and the CRF), clinical and office charts, laboratory and pharmacy records, diaries, radiographs and correspondence. All documents will be stored in confidential conditions. Any deviation from this must be explained appropriately.

For quality assurance purposes, the Consultant principal investigator at all participating sites will be asked to identify an independent person to validate a proportion of the submitted data. Overall, approximately 5% of the dataset selected at random will be independently validated. If concordance between the number of cases submitted on REDcap and those identified independently is <90%, the Unit's data will be excluded from the analysis. This is consistent with the quality assurance procedure used in other large collaborative audit projects[66].

7. Data management and storage

Data collection will occur in accordance with GCP, Caldicott principles and the General Data Protection Regulation (GDPR) 2018, and will work in line with NHS confidentiality guidelines and codes of conduct. Data for each patient will be pseudonymised using a unique

alphanumeric study identification number. No patient identifiable data will be recorded into the REDCap database and the CRF for the purpose of the study.

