Study data will be collected and managed using REDCap electronic data capture tools hosted at University of Manchester and made freely available to research collaboratives in the UK. REDCap (Research Electronic Data Capture) is a secure, web-based application designed to support data capture for research studies, providing 1) an intuitive interface for validated data entry; 2) audit trails for tracking data manipulation and export procedures; 3) automated export procedures for seamless data downloads to common statistical packages; and 4) procedures for importing data from external sources. More information about the consortium and system security can be found at http://www.projectredcap.org/.

The local PI will keep a secure record of the RedCap ID with corresponding NHS number (in England Wales), Community Health Index number (in Scotland), or Health and Care number (in Northern Ireland). This is required for the research team at each participating centres (Consultant PI, research nurse, and clinical trial assistants) to access the hospital electronic system at 3 and 5 years after LRR diagnosis to record the oncological outcome as specified in section 4.4.

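### Men are eligible, but the listed dataset has no item for sex and the menopausal item has no valid answer for a man

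*Protocol*

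**What the plan says.** Section 4.6.1 opens eligibility to "Female or male patients more than 18 years old".

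Section 5 then sets out the dataset item by item. Part 1 is introduced with "Patient demographics (at the time of LRR diagnosis) collected will include" and has seven items: centre, age, menopausal status, BMI, smoking, performance status and family history risk. The menopausal item reads "1.3 Current menopausal status (pre-menopausal, post-menopausal, perimenopausal", and those three states are its only options. Other items do allow for patients to whom they do not apply; item 2.5, for example, asks "was MRI performed (Yes/No/Not applicable".

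Section 6 states "All fields MUST be completed" and requires submitted data to be checkable against source records. The same paragraph ends "Any deviation from this must be explained appropriately".

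On identifiability, section 7 says "No patient identifiable data will be recorded into the REDCap database and the CRF for the purpose of the study". It also says "The local PI will keep a secure record of the RedCap ID with corresponding NHS number (in England Wales", with the equivalent numbers for Scotland and Northern Ireland, so that sites can reopen records at 3 and 5 years.

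**The concern.** Both sexes are admitted by an explicit choice, but the data list appears to be written for women only. Two consequences follow.

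First, sex is a basic descriptor of a cohort. Section 2.3 sets out to study risk factors for locoregional recurrence and prognostic factors for outcome, and section 8 plans regression to control for predictive variables. A variable that is not collected cannot serve any of these purposes. A statistical analysis plan can choose covariates and subsets, but it cannot supply a field that the form does not hold.

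Second, a man has no correct answer to item 1.3. Different sites may handle this differently, and the analyst would have no way to see which entries are affected. Any summary by menopausal status, including a summary of the endocrine treatments the study records, would then mix in some men.

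**Working it through.** The Protocol states no figure on this point, so there is none to reproduce. The check is a reading of the item list, followed by simple arithmetic on an assumed share of men.

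**Step 1: is sex recorded anywhere?**

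| Part of the dataset | Items | Items recording sex |
|---|---|---|
| Section 5, part 1 (demographics) | 1.1 to 1.7 | 0 |
| Section 5, part 2 (original cancer) | 2.1 to 2.39 | 0 |
| Section 5, part 3 (recurrence) | 3.1 to 3.52 | 0 |
| Section 4.4 (outcomes at 3 and 5 years) | all | 0 |

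**Step 2: can a man answer item 1.3?** None of its three options is valid for a man. The list offers a not-applicable answer elsewhere (items 2.5, 2.23, 3.40 and 3.42), so the device was available and was not used here.

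**Step 3: what can a site do?** Set against the rules in section 6, there are two routes:

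- Choose one of the three states. The field is complete, but the entry is untrue and cannot be checked against source.
- Leave the field blank, perhaps with an explanation. The entry is honest, but it breaks the completion rule as written, and no code is given to mark why.

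A blank in item 1.3 is also harder to interpret than a blank in a conditional item. If item 2.8 (sentinel node localisation method) is empty, item 2.7 (type of axillary surgery) shows whether it applied. Item 1.3 has no such parent, because the parent would be sex. A blank could mean a man or a missing value.

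**Step 4: would routine validation catch it?** Not reliably. Section 6 has about 5% of the dataset checked, and its exclusion threshold concerns agreement in the number of cases, not the content of this field.

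**Step 5: how many patients?** The Protocol gives no share of men, so 0.5% to 2% is an assumption. The totals of 500 (recruitment target) and 330 (needed for the primary comparison) come from section 8. Expected men = share × total:

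| Assumed share | of 500 | of 330 |
|---|---|---|
| 0.5% | 0.005 × 500 = 2.5 | 0.005 × 330 = 1.65 |
| 1% | 0.01 × 500 = 5 | 0.01 × 330 = 3.3 |
| 2% | 0.02 × 500 = 10 | 0.02 × 330 = 6.6 |

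Rounded, that is about 3 to 10 patients overall and 2 to 7 in the primary comparison.

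**The case against.** **The completion rule cannot be literal.** Items 2.8, 2.24, 2.29, 3.11 and 3.28 are conditional and have no not-applicable option, so some patients cannot answer them. The workable reading is that applicable fields must be completed, and section 6 allows explained deviations. This stands. A reader might infer that every man will be given a false menopausal category; the Protocol does not support that, because a blank with an explanation is possible. What remains is that the handling is left to each site.

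**Men can be traced.** Section 7 keeps the link from study ID to health service number at each site. This also stands. A reader might infer that men can never be identified once entered, but a site query would find them. The narrower point holds: the central data as listed do not identify them, and no query is planned.

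**The built form is not shown.** The wording that introduces the demographics need not be exhaustive, and a sex field would not conflict with the bar on identifiable data. The REDCap form may already contain one. That is possible, and the fix allows for it, but section 5 is the specification available and it omits the field.

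**The link to the primary comparison is thin.** The Protocol says nothing about the share of men, their original surgery or their prognosis. The covariates named in section 8 are tumour and nodal staging, receptor profile and grade, so a wrong menopausal entry does not enter that adjustment. With 2 to 7 men in 330, a sex effect could hardly be estimated. This stands and limits the weight of the point.

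**Conclusion.** The point holds as a minor data-capture gap. The Protocol admits men, lists no item for sex, and gives a man no valid answer to a menopausal item that it treats as compulsory. His record will hold either an untrue category or an improvised blank. From the central data as listed, the sex distribution cannot be reported, sex cannot be examined as a prognostic factor, and the comparison of original surgery types cannot be limited to women without going back to sites.

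The size is small: about 3 to 10 of 500 patients, or 2 to 7 of 330, on an assumed share of 0.5% to 2%. The effect on the primary estimate is probably small as well. A reader might infer that the comparison is biased because men would fall mainly in the mastectomy group. That is an assumption for which the Protocol offers no figure, and the conclusion here does not depend on it. The conclusion does depend on section 5 being a fair picture of the form in use.

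**What to change.** - Add an item for sex (female/male) to section 5, part 1.
- Add a 'not applicable (male)' option to item 1.3.
- For patients already entered, ask each site to supply sex through its local ID key and to correct item 1.3 where needed. The request could go out with the 3-year outcome return, when sites reopen the records anyway.
- If the built REDCap form already has both, amend section 5 to match it; no query is then needed.

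A rerun of the primary comparison in women only is optional and would probably change little.

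The cost is one field, one answer option and one site query. Eligibility does not change, and no patient contact should be needed.

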One of the key aim of the MARECA study will be to identify which patient groups are at most risk of further LRR, distant metastasis, and subsequent mortality after their treatment of LRR. A notable study in 2009 reported OS rates for patients with node negative cancer who were treated by BCS and WBRT as part of the NSABP protocols of node negative breast cancer[60]. They reported worse OS outcome in patients who presented with recurrences in the regional lymph nodes, as opposed to recurrences in the conserved breast (5 year OS of 34.9% versus 76.6% respectively). In addition, shorter interval time between the initial and recurrent cancer diagnosis has been identified as a poor prognostic factor for patients diagnosed with LRR[61]. By evaluating the tumour characteristics and treatment patterns of the initial and recurrent cancer, MARECA study will aim to identify other predictive prognostic factors for patients diagnosed with LRR. This will in turn guide clinicians with an aim of optimising patient management and improve treatment outcomes.

2. Aims and Objectives

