2.4 Study endpoints

2.4.1 Primary endpoint:

DFS following LRR resection in patients who present without distant metastasis, stratified according to the type of surgery performed for the primary breast cancer (BCS and radiotherapy vs. mastectomy).

2.4.2 Secondary endpoint:

-PFS in patients who present with LRR with distant metastasis.

-OS in patients with LRR +/- DM at presentation.

3. Definitions

For the purpose of this study, LRR is defined as diagnosis of invasive breast cancer or ductal carcinoma in situ in the ipsilateral breast (if applicable)/skin/chest wall/regional nodes (axilla/internal mammary/supraclavicular/infraclavicular) following previous breast cancer treatment with curative intent.

4. Methods

This is a prospective observational multicentre longitudinal cohort study. This will be a national research study in collaboration with the Association of Breast Surgery (ABS) Academic and Research committee, the Mammary Fold Academic and Research Collaborative (MFAC) committee, and the UK Breast Cancer Trainees Research Collaborative Group (BCTRCG).

The study will have 3 main phases;

- 1. National practice questionnaire on current management of patients diagnosed with LRR by breast MDTs across UK.
- Development of a national prospective cohort of patients newly diagnosed with LRR
 +/- DM in order to document management details for each patient with respect to their original and recurrent cancer.
- 3. Evaluating oncological outcomes of the study cohort at 3 and 5 years by collation and analysis of the data submitted from the participating centres.

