- 2.8 If sentinel lymph node biopsy, method of localisation (dual technique with blue dye and radioisotope / radioisotope alone / blue dye alone / other methods)
- 2.9 Was the original breast cancer inflammatory breast cancer (Yes/No)

Pathology

- 2.10 Tumour subtype (invasive ductal / invasive lobular / mixed ductal and lobular / other subtypes / pure ductal carcinoma in situ)
- 2.11 Tumour grade (1 to 3 for invasive / low to high grade for ductal carcinoma in situ)
- 2.12 Tumour size (in mm; invasive tumour size, unless DCIS)
- 2.13 Multifocal or multicentric cancer (Yes/No)
- 2.14 Lymphovascular invasion (Yes/No)
- 2.15 Closest radial margin after final surgery (in mm)
- 2.16 Were anterior or posterior margins close (1mm or less)? If Yes, please state which (anterior / posterior / both) and distance in mm (0,1)
- 2.17 Number of positive axillary nodes (state macro- or micrometastasis)
- 2.18 Number of axillary lymph nodes retrieved
- 2.19 Oestrogen receptor Allred score (ER; 0 to 8; please state if any other scoring system was used and its score; e.g. H-score)
- 2.20 Progesterone receptor Allred score (PR; 0 to 8; please state if any other scoring system was used and its score; e.g. H-score)
- 2.21 HER2 receptor status (Positive or negative; please state immunohistochemistry score 0/1+/2+/3+; if 2+ was FISH test done? What was the final HER2 receptor status if FISH test done; positive/negative/not applicable)
- 2.22 Ki67 test? If Yes, please state %

Adjuvant treatment

- 2.23 Receipt of radiotherapy after breast conserving surgery or mastectomy (Yes/No/Not applicable)
- 2.24 If radiotherapy after breast conserving surgery, please state radiotherapy regimen (whole breast radiotherapy; 40 Gy in 15 fractions / whole breast radiotherapy; 27Gy in 5 fractions (hypofractionated) / partial breast radiotherapy / whole breast radiotherapy with boost)
- 2.25 Radiotherapy to the axilla (Yes/No)
- 2.26 Supraclavicular fossa radiotherapy (Yes/No)
- 2.27 Internal mammary node radiotherapy (Yes/No)
- 2.28 Receipt of adjuvant endocrine therapy (Yes/No)
- 2.29 If receiving or received endocrine therapy, please state duration received (total number of years)
- 2.30 Please state first line endocrine therapy (tamoxifen / letrozole / anastrozole / exemestane / ovarian suppression / others; please specify)
- 2.31 What was the duration of the first line endocrine therapy? Please state number of years

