Descriptive summary statistics will be calculated for each outcome and regression analysis used to control for predictive variables. Data will be tested for distribution and differences between groups using unpaired t-tests, Mann-Whitney U tests and Chi squared tests as appropriate. Based on the NCRAS report described in section 1, approximately 250 patients were diagnosed with LRR with or without distant metastasis across 15 UK breast units over 6 months. This data suggests that around 33 patients will be eligible for recruitment over 12 months in each breast unit. This potential sample size has been corroborated from data at Leeds Teaching Hospitals NHS trust (LTHT) where 28 patients met the eligibility criteria (January 2019 to December 2019). This was based on information from the LTHT cancer information team. There are 144 breast units in the UK and at least 50 units so far have agreed to participate in the study. Given the variable number of cancer patients treated per year in these participating units, we would anticipate each unit to recruit 5 to 10 patients over 12 months. Therefore, we would aim to recruit at least 500 patients diagnosed with LRR +/distant metastasis over 24 months. There are no statistical criteria for stopping the study early as the study is observational in nature examining current UK practice and therefore low risk.

One of the key aim of the study is to determine whether patient prognosis after their LRR diagnosis (without distant metastasis) differs according to the type of breast cancer surgery (mastectomy versus BCS and radiotherapy) for the initial cancer. Based on published studies[36, 37, 39], the distribution of patients presenting with LRR is almost even between mastectomy and BCS for the initial cancer (40% mastectomy and 60% BCS). From these published studies, the 5 year DFS after treatment for LRR has been reported to be approximately 70%[67, 68]. A single centre retrospective study by Shenouda *et al*[39] identified that patients initially treated with BCS and radiotherapy had improved DFS by

approximately 20% as compared to patients initially treated with mastectomy and no radiotherapy (5 year DFS of 80% vs. 60%).

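### Where radiotherapy comes later than month 3, the BCS-and-radiotherapy group loses recurrences that precede it and the mastectomy group does not: a selection by interval, probably small

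*Protocol*

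**What the plan says.** - **Entry.** Protocol section 4.6.1 requires "A *minimum of 3 months interval* between the resection surgery for the original cancer and the diagnosis of locoregional recurrence". There is no upper limit, and the rule does not depend on radiotherapy.
- **Groups.** Section 2.4.1 has the primary endpoint "stratified according to the type of surgery performed for the primary breast cancer (BCS and radiotherapy vs. mastectomy"). The first group needs a treatment given after the operation; the second does not.
- **Time origin.** The endpoint is "DFS following LRR resection in patients who present without distant metastasis".
- **Exposure data.** Section 5, item 2.23, asks for "Receipt of radiotherapy after breast conserving surgery or mastectomy (Yes/No/Not applicable"). Item 2.24 adds the regimen after BCS. Neither the date of radiotherapy nor whether it had been planned is collected.
- **Prognosis.** Section 1.5.4 states that a "shorter interval time between the initial and recurrent cancer diagnosis has been identified as a poor prognostic factor".
- **Analysis.** Section 8 names stage, receptor profile and grade as covariates for the power calculation. For the Cox model it refers only to potential prognostic factors.
- **Dates.** The date of original surgery (item 2.1) and of LRR diagnosis (item 3.1) are both collected.

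**The concern.** Membership of the BCS-and-radiotherapy group depends on not recurring before radiotherapy has been given. Membership of the mastectomy group carries no such condition. Suppose two patients recur five months after surgery, one after mastectomy and one after BCS with radiotherapy still to come. Both meet the entry criteria. The first is counted as mastectomy. The second is coded No in item 2.23 and, on the wording of section 2.4.1, belongs to neither group.

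On the protocol's own account, short-interval recurrences do worse. Removing some of them from one side only would raise that side's DFS for a reason unrelated to the type of surgery, and in the direction of the planning assumption (80% after BCS and radiotherapy, 60% after mastectomy). Because this comes from the group definition, a larger sample would not reduce it.

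The cited study behind the planning difference describes its comparator differently, "compared to patients initially treated with mastectomy and no radiotherapy". If the mastectomy group were read that way, mastectomy patients who recurred before planned radiotherapy would be held in it, which would add to the effect.

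**Working it through.** No figure in the protocol states this effect, so there is none to reproduce. The sample size (165 per group, 330 in total) does not bear on the point, except that 330 at the protocol's 40:60 split gives 132 mastectomy and 198 BCS patients.

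**Inputs from the protocol (section 8):** 5-year DFS of about 70% overall; planned difference 80% − 60% = 20 points; split 40:60.

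**Assumptions, not in the protocol:**
- *f*, the share of recurrences diagnosed after month 3 but before radiotherapy
- *d*, the DFS gap between later and early recurrences
- no true effect of surgery, and the same *f* and *d* in both source populations
- every BCS recurrence in the window is lost, which makes the results upper values for a given *f* and *d*

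**Step 1: plausible f.** With a constant recurrence rate from month 3 to a horizon of H months, and radiotherapy at month e, f = (e − 3)/(H − 3).

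| Radiotherapy at month | H = 60 | H = 120 |
|---|---|---|
| 6 | 3/57 = 5.3% | 3/117 = 2.6% |
| 8 | 5/57 = 8.8% | 5/117 = 4.3% |
| 12 | 9/57 = 15.8% | 9/117 = 7.7% |

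If radiotherapy is given by month 3, f = 0 and the effect vanishes. A recurrence rate concentrated soon after surgery would raise f.

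**Step 2: spurious difference.** With DFS L in later recurrences, BCS and radiotherapy reads L and mastectomy reads (1 − f)L + f(L − d) = L − fd. The difference is fd.

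| f | d = 20 points | d = 40 points |
|---|---|---|
| 2% | 0.4 | 0.8 |
| 5% | 1.0 | 2.0 |
| 10% | 2.0 | 4.0 |

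Against 20 planned points this is 0.4/20 = 2% to 4/20 = 20%. An extreme case, f = 15% with d = 60, gives 9 points. The mastectomy patients who drive it number 132 × f = 2.6, 6.6 and 13.2 for f = 2%, 5% and 10%.

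**Step 3: effect on the test.** Take 132 against 198 patients, L = 70%, no true effect and a two-sided 5% test of two proportions. SE = √[0.21 × (1/132 + 1/198)] = 0.0515, and P(reject) = Φ(fd/SE − 1.96) + Φ(−fd/SE − 1.96).

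- fd = 0.008: 5.3%
- fd = 0.02: 6.7%
- fd = 0.04: 12%
- fd = 0.09 (extreme case): 42%

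**The case against.** - **The loss is conditional.** It needs radiotherapy later than month 3, and the protocol gives no timing. Where radiotherapy comes earlier, the entry rule removes the same early recurrences from both groups. This stands, and the effect should be described as possible. The 3-month criterion is therefore not itself an error, although a reader might infer that; it narrows the asymmetry. The weak point is the group definition in section 2.4.1.
- **It is not immortal time.** A reader might infer guaranteed event-free follow-up. The protocol does not support that: DFS starts at LRR resection, after the group is fixed. What remains is a difference in case mix by interval.
- **The net direction is not established.** Section 1.2.2 describes omission of radiotherapy in older, low-risk patients. The same definition leaves those BCS patients out as well, and they may do well. This stands. It does not cancel the problem, since one exclusion follows a treatment choice and the other follows the recurrence itself.
- **Grouping by treatment received is legitimate** for a prognostic question in patients who already have LRR. That is fair, and a reason to leave the primary analysis set alone.
- **Restriction to resected patients without metastasis** may already remove some of the worst early cases from both groups. This too is fair.
- **The Cox model may adjust for interval.** Section 8 leaves room for it and both dates exist. This stands in part. In the pre-radiotherapy window there are no BCS-and-radiotherapy patients, so adjustment there is extrapolation. Item 2.23 also cannot separate radiotherapy omitted as unnecessary from radiotherapy overtaken by recurrence, and no analysis plan can recover that distinction from the listed dataset.

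**Conclusion.** The asymmetry is real on the protocol's wording: one group is conditional on a later treatment, the other is not, and entry is tied to surgery alone. Where radiotherapy falls after month 3, the resulting selection by interval tends to favour BCS and radiotherapy. Its size is probably small: 0.4 to 4 DFS points against 20 planned, for f of 2% to 10% and a gap of 20 to 40 points, none of which the protocol supplies. At a 40-point gap the false-positive rate would rise from 5% to between 5.3% and 12%. The upper end needs a wide window: under a constant rate over five years, f = 10% means radiotherapy at about month 8.7 (3 + 0.10 × 57) in every BCS patient.

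A reader might conclude that the primary comparison should be restricted to recurrences at least 12 months after surgery. The protocol does not support this. It gives no basis for that cut-off, and under the constant-rate assumption the restriction would remove 7.7% to 15.8% of 330, about 25 to 52 patients, including the short-interval cases whose prognosis the study wants to understand. This is a cheap improvement to the data and the sensitivity analyses. It does not call for a change of design or sample size.

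**What to change.** Keep the eligibility criteria and the primary analysis set. Then:

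1. Add to item 2.23 the answer *planned, not given because LRR was diagnosed first*. Section 4.2.2 already has sites review clinic letters and MDT recommendations, so the answer can be taken from existing records.
2. Add a by-intention sensitivity analysis in which these patients are counted with the BCS-and-radiotherapy group.
3. Name the surgery-to-LRR interval (item 3.1 minus item 2.1) among the Cox covariates.
4. Add a sensitivity analysis that applies one common, later minimum interval to both groups, at more than one cut-off.

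The cost is one more answer option, a little more analysis, and fewer patients in the common-interval sensitivity analysis only.
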